The sample size calculation is based on the expected percent of men engaging in high risk behavior after 6 months of follow-up, accounting for the intraclass correlation coefficient (ICC) and estimates of unprotected sex estimated from our pilot dataset of 105 participants from four barbershops. Unprotected sex, defined in this example as two or more sexual partners in the past three months plus at least one episode of unprotected vaginal or anal sex, was reported by 42% of our sample in a previous pilot study of the program. Assuming that 42% of the participants in the control group would engage in high risk behavior, an ICC of 0.03, and a minimum of 23 participants from each barbershop, the study has 80% power to detect an absolute reduction of 12% (relative reduction of 29%) in rates between the two groups with alpha=0.05, two-tailed and 15 barbershops for each intervention group (i.e., 30 clusters and 690 total participants). In order to achieve a sample size of 690 at the six-month follow-up, we estimate that we will need to recruit 875 men in order to account for a loss to follow-up as high as 20%.

Participants:

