Statistical analysis will be performed by SAS version 9.2 (SAS Institute, Cary, NC). The primary analysis method for study outcomes to test the main effect of the *Barbershop Talk* intervention will be generalized estimating equations (GEE) models, accounting for the cluster randomization. A logit link function will be specified for binary outcomes (including the primary outcome of engaging in high risk behavior after 6 months of follow-up) while a identity link function will be specified for continuous outcomes. The effects of mediating and moderating variables will be tested by appropriate modeling methods (Jaccard, Turrissi et al. 1990; Shrout and Bolger 2002; MacKinnon, Fairchild et al. 2007). Generalized mixed effects models, treating barbershop as a random effect, will also be fit as sensitivity analyses. All statistical tests will be at the 5% (two-tailed) significance level for main effects and at the 10% (two-tailed) significance level for interactions, with no adjustment for multiple testing.

Timeline:

This is a five year study. We will spend the first six months of the study working with our community advisory board on issues of protocol development, on development and production of high quality graphics for the program, on training of study staff, on securing of IRB approvals for the work and recruiting barbershops. Given our past experience in the barbershops, and our recruitment goal of 875 men, we anticipate that we will enroll participants at the rate of 20-25 per month over a forty-two month period. This would carry our follow-up period through to month six of year five. In the last six months of year five, we will engage in data cleaning and analysis, and dissemination of research findings.

Human subjects considerations:

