## **STATISTICAL ANALYSIS PLAN**

Project Title: Barbershop Talk: HIV Prevention for African American Heterosexual Men

NCT Number: NCT01980771

Date of document: 8/16/18

To describe study sample characteristics across groups at baseline and follow-up and in relation to condomless sex, the  $\chi^2$  test for categorical variables and the independent samples t-test for group differences in continuous variables were utilized. From the original list of measured variables, only those covariates that were associated at  $p < 0.05$  with baseline report of condomless sex or on which there were imbalances between the BTWB intervention and control groups at baseline, were included. Generalized mixed-effects models were used to estimate between-group differences at the participant level, taking into account the hierarchical data structure, with men clustered by barbershop. Differences between the BTWB intervention and control groups in changes in the outcomes were analyzed on an intention-to-treat basis. A binary logistic regression model was used to examine changes in condomless sex, with the six-month value modelled as the outcome and experimental group as the predictor, while controlling for barbershop site of recruitment (random effect), the baseline value of condom use (fixed effect), and covariates (fixed effects). Interaction terms between the covariates and experimental group assignment were tested for statistical significance in a stepwise approach. Data were analyzed using SAS PROC GLIMMIX, version 9.4, 2013.

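### With 30 shops, neither the protocol's GEE nor the SAP's GLIMMIX model states a small-sample variance correction or denominator df; an uncorrected GEE Wald test would run at about 7% or more, the mixed model at about 5% to 7.5%

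*Protocol*

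**What the plan says.** The protocol (Study design and sample size) randomises shops rather than men and plans 15 shops per group, that is "30 clusters and 690 total participants". Its inputs are "an ICC of 0.03, and a minimum of 23 participants from each barbershop".

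The protocol (Data analysis) makes "generalized estimating equations (GEE) models, accounting for the cluster randomization" the primary method, with a logit link for binary outcomes, and offers a mixed model with a random shop effect as a sensitivity analysis. On error control it says "All statistical tests will be at the 5% (two-tailed) significance level for main effects".

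The SAP, dated 8/16/18 and written in the past tense, does not mention GEE. It describes a logistic model for the six-month outcome with a random shop effect and fixed effects for the baseline value and covariates, and closes with "Data were analyzed using SAS PROC GLIMMIX, version 9.4, 2013".

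Neither document names a variance estimator, test statistic, reference distribution, estimation method or denominator df. They do not rule a correction out; they are silent.

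**The concern.** Arm does not vary within a shop, so however many men are enrolled, the information on the arm effect comes from differences between 30 shops. Two large-sample habits then do harm. The ordinary sandwich variance is biased downward with few clusters. A normal critical value, or one on several hundred residual df, ignores the uncertainty in a between-shop variance estimated on 28 df. Both make p-values too small and intervals too narrow.

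At stake is whether the two-sided 5% promised for main effects is what the analysis delivers. Because the options are open, a borderline result could fall on either side of 0.05 depending on a software choice that nobody wrote down. The protocol also applies GEE to its continuous outcomes, so the gap is not confined to the primary endpoint.

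**Working it through.** **Inputs.** From the protocol (Study design and sample size): 15 shops per arm, 23 men per shop, ICC 0.03, control rate 42%, target difference 12 points (42% versus 30%), two-sided alpha 0.05, stated power 80%. Shop-size variation is not given. The protocol (Recruitment procedures) expects enrolment roughly in proportion to each shop's client pool, so CVs from 0 to 0.9 around a mean of 23 are assumed. The SAP gives no outcome rate, ICC or cluster count, so the protocol's values are used for its model too.

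**1. The plan's own power figure.** Design effect = 1 + (23 − 1) × 0.03 = 1.66. Men per arm = 15 × 23 = 345. SE = √[(0.42 × 0.58 + 0.30 × 0.70) × 1.66 / 345] = √(0.4536 × 1.66 / 345) = 0.0467. Then 0.12 / 0.0467 = 2.57, and power with a normal critical value is Φ(2.57 − 1.96) = 72.9% (72.3% with a pooled variance). With t on 28 df it is 69.8%. The stated 80% does not reproduce. That is a separate matter; here the calculation only prices the correction.

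**2. GEE Wald z, equal shops, closed form.** With K = 15 equal shops per arm, the uncorrected sandwich divides the between-shop sum of squares by K² where the unbiased estimator divides by K(K − 1). The variance is therefore too small by the factor 14/15, and the SE by √(14/15) = 0.966.

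- Normal instead of t(28) critical value alone: 2P(t28 > 1.96) = 6.0%.
- Both faults together: 2P(t28 > 1.96 × 0.966) = 2P(t28 > 1.893) = 6.9%.
- Interval width relative to a correct one: 1.893 / 2.048 = 0.924, so about 8% too narrow.

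**3. GEE by simulation under the null.** Beta-binomial outcomes at 42%, ICC 0.03, 15 + 15 shops, 60,000 to 100,000 replicates (Monte Carlo SE about 0.1 point), no covariates:

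| Shop-size CV | Uncorrected Wald z, independence weights | Kauermann-Carroll, t(28) | Mancl-DeRouen, z |
|---|---|---|---|
| 0 | 6.8% | 5.0% | 5.2% |
| 0.5 | 7.4–7.6% | 5.3% | 5.3% |
| 0.7 | 8.1–8.2% | 5.6% | 5.4% |

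Repeat runs spanned 7.2% to 7.7% at CV 0.5 and 8.1% to 8.4% at CV 0.7. At CV 0.9 the uncorrected test reaches 9.0% to 9.2%. With exchangeable weights it is 6.6% to 7.4% over CV 0 to 0.9. An uncorrected robust score test gives 5.1% to 5.4% throughout.

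**4. Random-shop logistic model.** Same null, pseudo-likelihood fit, 8,000 to 12,000 replicates (Monte Carlo SE 0.2 to 0.3 point), no covariates, CV 0 to 0.9:

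| Estimation | Residual df (about 660) | 28 df |
|---|---|---|
| REML-type | 5.8–6.2% | 5.0–5.3% |
| ML-type | 6.3–7.5% | 5.3–6.5% |

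Over ICC 0.01 to 0.10, the REML-type fit with residual df runs from 5.0% to 6.7%.

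**5. Why the two sandwich corrections take different reference distributions.** With equal shops, Kauermann-Carroll multiplies the variance by 15/14, which exactly undoes the bias, so t(28) gives 5%. Mancl-DeRouen multiplies it by (15/14)², leaving the SE √(15/14) = 1.035 times too large. A normal critical value then gives 2P(t28 > 1.96 × 1.035) = 5.2%, as simulated.

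**The case against.** The strongest reply is that silence is not a method. The protocol says GEE with a logit link and the SAP says PROC GLIMMIX; neither says Wald, uncorrected sandwich or residual df. A GEE score test, or a REML-type mixed model with between-shop df, is close to nominal. This stands, and every figure above is conditional for that reason. It does not remove the point: the first document to fix the choice should be the plan, and an ordinary GEE Wald test is anti-conservative even with equal shops.

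Second, the later document does not use GEE at all, so the larger figures attach to a model that may not have been run. This also stands. A reader might infer that both planned analyses run at 6.5% to 8%. The documents do not support that for GLIMMIX: a mixed model uses a model-based variance, not the sandwich, and it reaches 6.5% or more mainly with ML-type estimation and residual df, which the SAP does not state.

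Third, the upper GEE figures need unequal shops, while the sample size section plans at least 23 men per shop and 30 × 23 = 690, which is equal shops exactly. The recruitment section does expect sizes to differ, but gives no CV. So 6.9% is the figure tied to the protocol's own inputs; 7.4% to 8% is a range under assumption.

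Fourth, the SAP model adjusts for baseline and covariates and the simulations do not. The residual ICC after adjustment is unknown, and 28 df is the planned value only.

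**Conclusion.** The point holds as an unspecified option with a calculable consequence. An uncorrected sandwich Wald z on the protocol's GEE would run at about 6.9% with equal shops, and about 7.4% to 8% at CV 0.5 to 0.7. For the SAP's mixed model the excess over 5% ranges from about nil (REML-type, between-shop df), through about 1 point (REML-type, residual df), to about 2.5 points (ML-type, residual df).

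These figures rest on 15 shops per arm, a 42% rate, ICC 0.03, assumed shop-size CVs and no covariate adjustment. They do not show that the 5% promise was broken, because the documents do not reveal which test was or would be used. The effect is moderate: it matters for a result near the threshold, not for a clear one.

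**What to change.** State the test of the arm effect in full.

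- **If GEE is kept:** use a small-sample corrected sandwich variance, Kauermann-Carroll or Mancl-DeRouen. With Kauermann-Carroll, refer the arm effect to a t distribution with shops minus 2 df (28 as planned, less one for each shop-level covariate).
- **If GLIMMIX is the analysis:** specify REML-type estimation, with between-shop or Kenward-Roger denominator df for the arm effect.
- **If the analysis is already done:** report the estimation, variance and df options that were used, and give the corrected result beside the reported one.

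The cost is a sentence in the SAP and one or two program options. Intervals widen slightly (about 8% with equal shops, against an uncorrected GEE Wald interval: 1 / 0.924 = 1.08). Planning power for 42% versus 30% is about 70% rather than 73%.

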All measures included in the program evaluation have been selected based on their demonstrated reliability and validity in published research and in our own previous work in populations similar to the men in this study; we will pilot the instrument prior to administration. To examine hypothesis 1, our main outcome measure will be a composite measure of the proportion of respondents who report two or more partners in the last six months and report unprotected sex during this time. This outcome, which was reported by over 40% of our population in our formative work, is a more informative marker of risk than some other outcome measures used in HIV prevention trials (e.g., any unprotected vaginal or anal sex) in that it helps to differentiate persons engaging in unprotected sex in the context of a single monogamous partnership, versus those who are at higher risk for HIV infection. Other measures of risk will include (1) partner concurrency, (2) number of sexual partners, (3) condom use consistency, and HIV testing. Behaviors will be assessed over the previous three months. Of course, self-report measures of sexual risk behavior are prone to self-report bias as individuals are likely to inflate or deflate their responses based on factors such as gender norms around sexual behavior. However, we will engage in a number of activities to promote honesty in responses by (1) assuring men of the confidentiality of their responses and explain the system that will be used to ensure this, (2) stressing the importance of honest answers to the scientific integrity of the project and for informing community health, (3) and using ACASI. Responses on this measure will be correlated with measures such as sexual behavior and drug use to provide an estimate of the extent to which this bias contributes to scores. Often, clinic-based interventions are able to collect data on more 'hard' outcomes, such as STD rates. The ability to power these studies is based on the fact that participants at baseline typically have and are treated for STD, and that there are known and substantial risks for 'repeat' infections in the control group. In our study, however, it would neither be feasible to conduct STD testing, nor acceptable to do so in the context of a community-based study involving barbershops. As described in our second hypothesis, our intervention is designed to directly influence a set of theoretically derived variables, which in turn are expected to influence sexual risk. These mediating variables include intrapersonal variables such as condom use and HIV testing attitudes, self-efficacy, and subjective norms, as well as perceived skills in communication and negotiation skills around safer sex. These measures are typically ordinal in nature but analyzed as having interval level properties measures

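### Number of sexual partners, a named secondary outcome, has no assured adjustment for its collected baseline count, which gives away precision but not validity

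*Protocol*

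**What the plan says.** Protocol, Program Evaluation: the main outcome for Hypothesis 1 is a "composite measure of the proportion of respondents who report two or more partners in the last six months and report unprotected sex". The text then adds: "Other measures of risk will include (1) partner concurrency, (2) number of sexual partners, (3) condom use consistency, and HIV testing". Number of partners is therefore a secondary outcome in its own right, and, cut at two, one of the two parts of the composite.

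Protocol, Data analysis: the primary method is GEE allowing for clustering by shop. "A logit link function will be specified for binary outcomes", "while a identity link function will be specified for continuous outcomes". Partner number is assigned to neither class, no count model is named, and no baseline term is mentioned. Mixed-effects models with shop as a random effect are a sensitivity analysis.

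SAP: the one model set out is a mixed logistic model for condomless sex at six months. Beside arm and shop it contains "the baseline value of condom use (fixed effect), and covariates (fixed effects". A covariate qualifies if it is associated at p < 0.05 with condomless sex at baseline, "or on which there were imbalances between the BTWB intervention and control groups at baseline, were included". Number of partners has no model of its own.

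**The concern.** A man's earlier number of partners should be among the better predictors of his later number. It is recorded by ACASI before the intervention, so using it needs no new data. Yet the Protocol's GEE text omits it, and the SAP admits it only through a screen that never asks whether it predicts the six-month outcome. Read literally, the default for this outcome is an unadjusted difference in means.

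At stake is power for a behaviour the program targets. Bias and type I error are not at issue.

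**Working it through.** **1. The plan's own figure.** None exists for number of partners. The only power statement (Protocol, Study design and sample size) is 80% for the binary composite: 42% v 30%, ICC 0.03, 15 shops per arm, 23 men per shop. There the design effect is 1 + 22 × 0.03 = 1.66 and the effective size 345/1.66 = 207.8 per arm. The two-sided pooled formula then gives 72.3%. That gap is a separate matter; only the layout of 30 × 23 = 690 men is used below.

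**2. What the link can change.** With only an intercept and arm, identity and log links both fit the two arm means. One tests their difference, the other the log of their ratio. Little change in power is expected.

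**3. What the baseline value can change.** Adjusting for a baseline with correlation ρ multiplies the variance by about 1 − ρ² (individual-level approximation). The documents give no ρ, so a range is shown:

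| ρ (assumed) | 1 − ρ² | 690/(1 − ρ²) |
|---|---|---|
| 0.2 | 0.96 | 719 |
| 0.3 | 0.91 | 758 |
| 0.5 | 0.75 | 920 |
| 0.7 | 0.51 | 1353 |

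**4. Simulation with a stable underlying rate.** Setting: 30 × 23 men, over-dispersed counts, baseline count at least 2, effect exp(−0.25) = 0.78, exchangeable GEE with bias-reduced standard errors, t on 28 df, 300 trials per row. Apart from over-dispersion and the intervention effect, each man's rate is the same at both visits, which favours adjustment. Power in %:

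| Observed correlation | Identity | Log | Identity + baseline | Log + log baseline |
|---|---|---|---|---|
| 0.18 | 67.0 | 66.7 | 73.0 | 73.3 |
| 0.35 | 46.3 | 47.3 | 54.3 | 56.3 |
| 0.42 | 59.7 | 60.7 | 74.7 | 74.0 |
| 0.66 | 66.3 | 66.7 | 90.3 | 91.0 |

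The link alone moves power by −0.3 to +1.0 points; baseline under identity adds 6 to 24. Monte Carlo error at 60% power is √(0.6 × 0.4/300) = 2.8 points. Null rejection was 3–5%.

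**5. Simulation in which the underlying rate changes between visits.** Same layout, Poisson-lognormal counts, 25% reduction, shop-robust t on 28 df, baseline at least 2, 1,000 trials per row. The last model is negative binomial (NB). Power in %:

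| Log SD, latent correlation | Identity | Log | Identity + baseline | NB log + log baseline |
|---|---|---|---|---|
| 0.8, 0.4 | 82.9 | 84.0 | 86.9 | 88.4 |
| 0.8, 0.7 | 87.7 | 87.4 | 95.4 | 96.0 |
| 1.1, 0.4 | 56.1 | 57.5 | 62.1 | 65.9 |
| 1.1, 0.7 | 65.2 | 66.4 | 80.4 | 88.1 |

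- Link alone: +1.1, −0.3, +1.4, +1.2 points.
- Baseline under identity: +4.0, +7.7, +6.0, +15.2.
- Further gain from the count model: +1.5, +0.6, +3.8, +7.7.
- Null rejection: about 3–7% (600 trials).

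A further run with latent correlation 0.4–0.6 and the same log SDs gave under 1 point for the link, about 3–10 for baseline under identity and about 0–5 for the count model, with null rejection of 3–5%. That is the range quoted in the conclusion; the rows at 0.7 lie above it.

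**6. Truncation.** Eligibility requires at least two partners over six months, but Program Evaluation says behaviours are assessed over three. If the baseline count covers three months it can fall below two. Without truncation (log SD 1.1, correlation 0.7) the four figures were 47.9, 49.8, 69.0 and 78.6, so truncation is the cautious assumption there.

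**7. The composite.** Adding log baseline partner count beside baseline condom use, 42% v 30%, 3,000 trials per setting: 70.1 to 71.0, 69.7 to 71.5 and 71.3 to 73.7, gains of 0.9, 1.8 and 2.4 points.

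**The case against.** The plan is silent here rather than wrong. The Protocol never calls partner number continuous and rules out no other link. The SAP's covariate rule can admit the baseline count, and its wording about differences in change hints at some use of baseline. The identity-link GEE is valid, the outcome is secondary, and every power figure rests on assumed skew and correlation. Counts simulated on a log scale also suit the log model. All of this stands. It limits the size of the point but does not remove it, because no route assures the baseline count a place.

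A reader might infer that the identity link itself wastes power because a few men with many partners dominate the mean. The documents give no distribution that would show this. A log link also models arithmetic means, and with arm alone it fits the same two means; the unadjusted comparisons above confirm that it changes little.

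A reader might also infer that the primary analysis is materially weakened, since partner number is half of the Protocol's composite. The simulated gain there is 0.9–2.4 points. The SAP's stated model is for condomless sex, not the composite, and already contains the baseline of its own outcome.

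**Conclusion.** The point holds as a loss of precision for one secondary outcome. With log SD 0.8–1.1, latent correlation 0.4–0.6 and baseline truncated at two, all assumed, the missing baseline value costs about 3–10 points of power under the identity link. A log-link negative-binomial model with log baseline recovers about 0–5 more, mainly when skew is heavy. The link on its own is worth under 1 point in that range, and at most 1.4 points in any truncated setting tabulated. The baseline gain is larger if partner numbers are more stable between visits. Type I error is not affected. Priority is minor.

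**What to change.** In the Protocol's Data analysis section and in the SAP, state that number of partners at follow-up is always adjusted for its baseline value, whatever the covariate screen shows. Preferably use a log link with negative-binomial variance and log(baseline count + 1) as covariate, with either shop-robust standard errors or a shop random effect, and report the ratio of mean partner numbers. The + 1 allows for a zero count if the recall window is three months.

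The cost is a few lines of text and one covariate already collected; the SAP's SAS procedure can fit the model. The effect becomes a ratio rather than a difference. The SAP is dated 8/16/18 and written in the past tense, while the Protocol's retention statement puts study end at about January 2017 (five years before January 2022). If the model is chosen after the data were seen, it should be labelled so.

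Adding the baseline partner count to a model of the Protocol's composite is optional, for a gain of about 1–2 points. It does not apply to the SAP's condomless-sex model as written.

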Hypothesis 1: Compared to men assigned to an attention control condition, those exposed to the intervention will have lower levels of sexual risk behavior at a 3 and 6 month follow-up.

Hypothesis 2: Compared to men assigned to an attention control condition, those exposed to the intervention will have improved outcomes at 3 and 6 months, on theoretically derived mediators of sexual risk behavior, including interpersonal factors such as attitudes, self-efficacy, communication skills and perceived norms around safer behavior, as well as on factors such as increased individual and community empowerment and decreased HIV-related stigma.

Aim 2: To examine individual and contextual-level factors that explain variation in the efficacy of the intervention.

Hypothesis 3: Intervention impact will be moderated by individual and contextual level-factors such as higher perceived basic needs and housing instability, incarceration and substance use history, higher perceived racism, and traditional gender role norms and attitudes, such that intervention effects will be reduced among men with these risk factors.

Project Rationale:

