Audio Computer-Assisted Self-Interview (ACASI) will be utilized to collect self-reported data at baseline (pre-intervention) and also at 3- and 6-month follow-up from the date of completion of the *Barbershop Talk* program. Respondents will listen to headphones and questions will be provided by a recorded voice stored in computer memory. The responses will be entered by pressing on the computer's touchscreen. A privacy screen will be utilized so that other barbershop customers cannot view responses, and headphones with disposable covers will be used so that respondents can listen to questions and answer options. Prior to baseline questions being administered, participants will complete a series of 'warm up' practice items. During our formative work, we piloted the recruitment, screening, consent and baseline procedures described in this project on 78 men and have found them to be feasible to implement, acceptable to barbershop personnel and clients, and a sound method for maintaining privacy and confidentiality. Additionally, at the 6-month interview participants will be asked to complete an additional set of questions to help identify the need for future programs. These final questions will be administered by a study staff in an interviewer led format. Questions 1-3 of the questionnaire pertain to existing knowledge about PrEP, and interest to receive more information about PrEP. In conjunction with these questions, study participants will be offered a PrEP brochure to increase their knowledge about HIV prevention. For question #4 of the interview a response card will be handed to study participants to facilitate the selection of their answers to that question. Participants will be reimbursed at \$20 for the baseline interview, \$30 for the three month follow-up assessment, and \$40 for the six month follow-up assessment, which is reasonable considering the length of the interview, and is in line with typical reimbursement levels for other HIV prevention program evaluations. The evaluation instruments will take approximately forty minutes to complete. All measures described in the following section have been selected based on their established reliability and validity in published HIV prevention studies and with adult African American populations.

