Evaluation assessments will take place via ACASI, with all other data forms (e.g., locator, enrollment, contact logs, and final interview questions) completed manually. For the linked baseline, 3, and 6 month assessments, we will assign each study participant a unique study identification number and their name and study ID number will be linked on a Locator Form (which will provide detailed contact information for follow-up, and will help reduce the of participants enrolling more than once), on an Enrollment Log (which will provide date and location of enrollment and scheduled interviews), on a Contact Log (which will document contacts of the client with data collection staff) and in the local data management system. Locator Forms, Enrollment Logs, signed Consent Forms, and Contact Logs will be kept in locked file cabinets in a locked office in SUNY DMC. Data transmission will be tracked and monitored by the project coordinator. ACASI interview data will be encrypted during the ACASI interview as information is captured and saved on the computer's hard drive, which will be transmitted to the project coordinator daily. Computer programs will be developed to check data completeness and consistency. Each system file will have its own system dictionary containing variable names, labels, valid code values and labels and missing data definitions. The SUNY IS Division performs nightly automated backups on a Digital Linear Tape system. In addition, once each month a complete backup tape is made for offsite storage. All data stored on the servers are password protected and encrypted.

Data analysis:

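### No stated model adjusts the continuous Hypothesis 2 scales for their own baseline scores; if they are analysed without that term, precision is given away

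*Protocol*

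**What the plan says.** Hypothesis 2 (Protocol, Aims and Hypotheses) is an arm comparison: it expects "improved outcomes at 3 and 6 months, on theoretically derived mediators of sexual risk behavior", and lists attitudes, self-efficacy, communication skills, perceived norms, empowerment and stigma. Program Evaluation says that the attitudinal and similar measures are treated as interval-level, and that ACASI collects "self-reported data at baseline (pre-intervention) and also at 3- and 6-month follow-up". Data management links the three assessments for each man by study ID. On a plain reading, each man's baseline score on each scale is therefore on file.

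For the analysis, the Protocol (Data analysis) gives GEE accounting for the cluster randomization, and "a identity link function will be specified for continuous outcomes". Mixed models with barbershop as a random effect are sensitivity analyses. No covariates are named for any outcome.

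The SAP writes out one outcome model, a logistic mixed model for six-month condomless sex. It controls for barbershop, "the baseline value of condom use (fixed effect), and covariates (fixed effects"). Covariates are kept if they are associated at p < 0.05 with baseline condomless sex, or if the arms are imbalanced on them at baseline. A general sentence adds: "Differences between the BTWB intervention and control groups in changes in the outcomes were analyzed on an intention-to-treat basis". The SAP gives no model for any Hypothesis 2 scale.

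**The concern.** A scale measured before and after the program usually predicts itself, so its baseline score is the obvious covariate for its follow-up score. The SAP uses this device for condomless sex but does not extend it in writing to the scales.

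The covariate rule does not close the gap. It looks at association with baseline condomless sex and at imbalance between arms. What matters for precision is how well a scale's baseline predicts that scale's follow-up, and the rule never looks at that. A scale's baseline could enter only by coincidence, and the only model shown with covariates is the one for condomless sex.

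The analyst is thus free to choose between follow-up scores alone, raw change scores and baseline adjustment, for at least six constructs at two follow-up times. Under the first two choices, Hypothesis 2 is tested with less power than the collected data allow. The primary binary outcome is not affected.

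**Working it through.** **The plan's own figure.** The documents state no power for the scales. The only power statement (Protocol, Study design and sample size) is 80% for the binary primary outcome. With its two-sided inputs (42% against 30%, design effect 1 + 22 × 0.03 = 1.66, effective 345/1.66 = 207.8 men per arm) I get about 72%, not 80%. That is a separate matter. Only the design values are borrowed here.

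**Inputs from the Protocol.** 15 shops per arm, 23 men per shop, two-sided alpha 0.05, ICC 0.03.

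**Assumptions, not in the documents.** The ICC of 0.03, given for the primary outcome, also applies to the scales. SDs are equal at baseline and follow-up. The baseline-to-follow-up correlation r is 0.3, 0.5 or 0.7. Effects are in SD units.

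**Follow-up only.** Variance of a shop mean: V0 = 0.03 + 0.97/23 = 0.0722. SE of the arm difference = √(2 × 0.0722/15) = 0.098 SD. Effect detectable with 80% power: (1.96 + 0.84) × 0.098 = 0.275 SD.

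**Own-baseline adjustment.** Two cases bracket the gain:
- Baseline explains within-shop variance only: V = 0.03 + 0.97(1 − r²)/23. At r = 0.5 this is 0.0616, a cut of 14.6%.
- Baseline explains both components: V = V0(1 − r²). At r = 0.5 this is 0.75 × V0, a cut of 25%.

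**Raw change score** (same r at both levels): V = V0 × 2(1 − r), which equals V0 at r = 0.5. The ratio of adjusted to change-score variance is (1 − r²)/[2(1 − r)] = (1 + r)/2, which is below 1 for any r below 1.

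**Power** = Φ(effect/SE − 1.96):

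| Effect | r | Follow-up only | Change score | Adjusted (within only to both) |
|---|---|---|---|---|
| 0.25 SD | 0.3 | 72.2% | 57.7% | 74.5–76.2% |
| 0.25 SD | 0.5 | 72.2% | 72.2% | 78.8–83.7% |
| 0.25 SD | 0.7 | 72.2% | 90.8% | 85.5–94.6% |
| 0.275 SD | 0.3 | 80.0% | 65.9% | 82.1–83.6% |
| 0.275 SD | 0.5 | 80.0% | 80.0% | 85.9–89.9% |
| 0.275 SD | 0.7 | 80.0% | 95.1% | 91.3–97.5% |

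The change-score column cuts both components, so compare it with the upper adjusted figure. On that footing adjustment gains about 18 points at r = 0.3 (76.2 against 57.7; 83.6 against 65.9), and only 2 to 4 points at r = 0.7 (97.5 against 95.1; 94.6 against 90.8).

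**Small-sample check.** With a t reference on 28 df and r = 0.5, power goes from 77.2% to 83.4–87.8% at 0.275 SD, and from 69.2% to 75.9–81.1% at 0.25 SD. The gain is of similar size.

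**Larger effects.** At r = 0.5, follow-up only against adjusted is 94.6% against 97.1–98.5% at 0.35 SD, and 98.3% against 99.3–99.7% at 0.40 SD. Little is left to gain.

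**The case against.** The strongest reply is that the SAP may already mean baseline adjustment. It speaks of examining changes in condomless sex, and the model it then describes has the six-month value as the response with baseline as a covariate. Read in that light, the plural in "Differences between the BTWB intervention and control groups in changes in the outcomes were analyzed on an intention-to-treat basis" could cover the scales in the same form. Raw change scores are specified nowhere. The Protocol's silence proves little either: it names no covariates even for the primary outcome, and does not say how the three linked assessments enter the GEE. All of this stands. A reader might infer that the scales were, or will be, analysed unadjusted and that precision is therefore lost. The documents do not support that. They show only that the adjusted form is not stated for the scales, so the loss is conditional.

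A second reply is that the size rests on a correlation, an ICC and effect sizes that the documents do not give for any scale, and that 0.25 to 0.275 SD is where power is most sensitive. That also stands. At r = 0.3 the gain over follow-up only is 2 to 4 points, and against change scores at r = 0.7 it is no larger.

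A third reply concerns chance baseline imbalance. The SD of the arm difference at baseline is about 0.10 SD, which at r = 0.5 would move an unadjusted follow-up difference by about 0.05 SD. A reader might count this as a further harm, or as bias. It is neither: it is already inside the 0.098 SE used above, and the randomized comparison is unbiased on average.

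None of these replies supplies the missing statement. The adjustment is at least as precise as either alternative under the assumptions shown, and it follows the SAP's own practice for condomless sex.

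**Conclusion.** The point holds as a gap in specification with a conditional cost. No stated model gives a Hypothesis 2 scale its own baseline term, and the covariate rule would not reliably supply one. If the scales are analysed on follow-up only, adjustment would add about 2 to 4 points of power at r = 0.3, 6 to 12 at r = 0.5 and 11 to 22 at r = 0.7, for effects of 0.25 to 0.275 SD. Against raw change scores the gain is large at r = 0.3 and about 2 to 4 points at r = 0.7. Over follow-up only, gains are small for effects of 0.35 SD or more. If the SAP's wording already means baseline adjustment, nothing is lost and only the text needs completing.

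These figures rest on the Protocol's 15 × 23 design, an ICC of 0.03 carried over to the scales, and an assumed r. The matter is precision of non-primary outcomes, not bias or type I error. The severity is low and the change is optional.

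**What to change.** In the Protocol's Data analysis section and in the SAP, state that each continuous Hypothesis 2 scale at 3 and 6 months is modelled with the follow-up score as the response, arm and the man's own baseline score on that same scale as fixed effects, and barbershop clustering retained. The baseline score enters whatever the covariate screen shows. Add a simple rule for a missing baseline score, such as mean imputation of that covariate.

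The cost is one sentence and one covariate per model. No new data or participants are needed, because the baseline assessment is already planned and linked to follow-up. The SAP is dated 8/16/18 and written in the past tense. If the analyses have been done in another form, refit them from the linked records and label the result as a refit, not as pre-specified.
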